**PI: [name]**

**NCT05374798**

**Document Date: October 4, 2024**

## SPECIFIC AIMS

Alcohol use disorder (AUD) and acute alcohol intoxication are well-established precipitants of intimate partner violence (IPV). Approximately one third of U.S. adults experience IPV during their lifetimes, with costs that exceed \$3.6 trillion in expenses. The health and financial burden of alcohol-facilitated IPV is particularly malignant, resulting in increased risk of mortality, morbidity, and poor treatment outcomes. Recent data also indicate that IPV negatively impacts AUD treatment and increases risk of relapse. While some promising outcomes from behavioral treatments for co-occurring AUD and IPV have emerged, findings are inconsistent and grow increasingly spurious following completion. Although behavioral treatments targeting AUD and IPV are effective for some women and men, efficacy is commonly limited by high dropout rates, poor working alliance, and low readiness to change. As a result, there is a critical and persistent need to develop dynamic treatment options to successfully reduce AUD and IPV concurrently.

Mitigating maladaptive physiological reactivity in the form of respiratory sinus arrhythmia measure of heart rate variability (HRV) is one promising pathway to achieve this goal. HRV is an autonomic biomarker of arousal relevant to AUD pathophysiology, alcohol consumption, and treatment outcomes. HRV is also an emerging mechanism underlying alcohol-facilitated IPV. Specifically, the combination of acute alcohol intoxication and emotional distress disrupt the central autonomic network's ability to regulate behavior, cognition, and emotion adaptively during couple conflict. Data from our group and others suggest that in controlled laboratory settings, alcohol intoxication and IPV are associated with acute elevations in heart rate and reduced HRV. For example, our team recently found that in a randomized controlled laboratory study using an alcohol administration paradigm, distressed violent couples demonstrated lower HRV compared to distressed non-violent couples (N=38) during intoxication and evocative partner stimuli compared to control conditions.

Growing evidence suggests that biofeedback interventions to modulate physiological, emotional, and behavioral stress responses are feasible, acceptable, and may reduce AUD symptoms such as craving to improve long-term AUD recovery. Our team extended this literature by conducting an exploratory pilot study among participants who had perpetrated IPV (N=4), and found that HRV biofeedback (HRV-B) conducted once daily for 10 days outperformed progressive muscle relaxation to restore normalized HRV. Taken together, this emerging data suggests that remote, self-administered biofeedback interventions hold promise as a discreet, accessible and low cost standalone or adjunct treatment option for AUD patients with high risk behaviors such as IPV. However, HRV has not yet been investigated as a mechanism of alcohol-facilitated IPV in naturalistic settings. Bridging this gap in the existing literature is essential to translate these promising laboratory findings into biomarker-driven treatment options to address this urgent public health problem. Thus, the primary objective of the proposed project is to use wearable technology to develop proof-of-concept of HRV as a biomarker of alcohol-facilitated IPV in naturalistic settings. Our secondary objective is to examine the preliminary usability, feasibility, and acceptability of a remote, self-administered HRV-B intervention.

To accomplish these goals, we will enroll a sample of 50 couples (100 total participants) with AUD and IPV into a 28-day micro-longitudinal study. Participants will wear activity trackers equipped with continuous ambulatory physiological monitoring and geolocation. Ecological momentary assessment (EMA; 4 times daily plus optional event-triggered reports) of alcohol use, couple conflict including IPV, and affect will be completed via smartphone application for 28 days. During days 22-28, participants will also be prompted to complete a 10 minute self-administered HRV-B session at least once daily. Subjective usability, feasibility, and acceptability of HRV-B will be assessed. The following Specific Aims are proposed:

**Specific Aim 1:** Employ a wearable physiological monitoring platform in combination with EMA and geolocation to examine the proximal role of HRV in alcohol-facilitated IPV among couples in naturalistic settings.

**Specific Aim 2:** Conduct a non-randomized, open-label pilot study examining the usability, feasibility, and acceptability of a remote heart rate variability biofeedback (HRV-B) intervention to reduce alcohol-facilitated IPV.

We hypothesize that episodes of alcohol use and IPV will be characterized by lower HRV as compared to episodes when neither alcohol use nor IPV occurs. We also hypothesize that HRV-B will demonstrate usability, feasibility, and acceptability as evidenced by use at least once daily and positive self-reported feedback. This translational study will advance the mechanistic science in this area by examining the proximal role of HRV in alcohol-facilitated IPV in naturalistic settings. This study has the added benefit of utilizing discreet wearable technology and geolocation to refine and optimize the content, dose, and timing of HRV-B. Findings will facilitate

the development of urgently needed just-in-time interventions that are personalized, accessible, and dynamic. The investigative team has the unique expertise necessary to implement this innovative study, which has the potential to yield essential public health impact. Findings will directly inform the design of a randomized controlled trial testing the efficacy of HRV-B to reduce alcohol-facilitated IPV through R01 series funding.

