**EMA Procedures.** Participants will download an application (provided by Illumivu, Inc.) on their mobile device. We will loan a compatible device and charger to participants who do not own one. Participants will complete a demo session (in person or via Doxy.me) with research staff to learn how to use the mobile device and EMA app and troubleshoot any challenges that arise. Four daily EMA reports will be requested via phone notification (Days 1-28; one morning report plus three subsequent reports at random times over the following 12 hours; i.e., one assessment per 4 hour time block). Participants will have the ability to select the time they receive the morning assessment and provide a daily window for start and end times. Both partners within each dyad will be assigned to the same assessment schedule. Participants will have 2 hours to complete the morning report and 30 minutes to complete subsequent reports, allowing flexibility to make up missed reports. Participants will also be instructed to complete event-driven reports if alcohol use or partner conflict occurs. Reports will include drinking and drug use, self and partner conflict behaviors, and subjective mood and affect. Research staff will contact participants by phone or text if the first two EMA entries on any particular day are missed.

**Physiological Assessment and Geolocation.** Participants will be issued a Garmin Vivosmart 4 activity tracker and charger and instructed to wear it continuously for 28 days of participation. We will instruct participants to charge the device during sleep to minimize disruption in data collection (60-90 minutes). No participant action is needed to store data from the tracker. EMA data is fully integrated with physiological data and geolocation using Illumivu's cloud-based server. This procedure will allow us to establish temporal sequence and both acute and lagged associations between HRV, drinking, and IPV, and to contextualize findings with geolocation. HRV measurements will be mean-centered for each participant in order to account for participants' baseline ("state"). *Illumivu, Inc. will provide cleaned data and peak, low, and average HRV for each 4-hour EMA assessment period.*

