## STATISTICAL ANALYSES.

**General.** All data will be collected in a REDCap database to ensure accuracy and validity and analyzed using SAS v9.4 (Cary, NC). Descriptive and summary statistics will characterize the sample and outcomes.

**Power and Sample Size.** Based on our enriched recruitment plan of couples with current AUD and IPV, and EMA studies of both healthy community couples and participants with IPV, we expect  $\geq 50\%$  of the couples enrolled in this study to report psychological or physical IPV during the 28-day study timeframe. Within-couple correlation of variables (HRV, alcohol use, IPV) will result in an effective sample size between  $N=50$  (the number of couples) and  $N=100$  (the number of individual participants). For example, for a within-couple intraclass correlation coefficient (ICC) of 0.1 or 0.3, sample sizes approximate  $N=90$  and  $N=76$ , respectively. At a minimum, the planned sample size conservatively provides 80% power to detect within-subject differences in HRV equivalent to Cohen's  $d$  effect sizes of 0.3 (the detectable difference with 1 paired set of observations on the  $\geq 50\%$  of subjects expected to report alcohol use and IPV), consistent with those observed in our preliminary studies (see Figure 1). However, given the volume of EMA data collected and despite the fact that many EMA reports will not involve alcohol or IPV, we may even be able to detect much smaller differences. For comparisons between partners within a dyad, we anticipate that effect sizes as small as 0.4 and correlations as small as 0.4 will be detectable with 80% power. Having  $N=100$  participants will also provide 85% power to detect whether feasibility and acceptability metrics are lower than 80%. These power analyses assume 2-sided testing and an alpha level of 0.05.

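### The only stated HRV hypothesis compares alcohol use and IPV with neither; on that contrast alone, a marker of drinking cannot be told from a marker of alcohol-facilitated IPV

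*Combined protocol and SAP*

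**What the plan says.** All references are to the combined protocol and SAP.

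- **Specific Aims, hypotheses.** The one HRV hypothesis is that "episodes of alcohol use and IPV will be characterized by lower HRV as compared to episodes when neither alcohol use nor IPV occurs". The other hypothesis concerns usability, feasibility and acceptability of the biofeedback.
- **Specific Aims, primary objective.** The study is to "develop proof-of-concept of HRV as a biomarker of alcohol-facilitated IPV in naturalistic settings".
- **Specific Aims, rationale.** Laboratory data are cited to the effect that "alcohol intoxication and IPV are associated with acute elevations in heart rate and reduced HRV". The proposed mechanism is that "the combination of acute alcohol intoxication and emotional distress disrupt the central autonomic" network's regulation of behaviour during couple conflict.
- **Physiological Assessment and Geolocation.** The data are to establish temporal order and "both acute and lagged associations between HRV, drinking, and IPV". No contrast or model is named. "HRV measurements will be mean-centered for each participant", which points to a within-person comparison.
- **Power and Sample Size.** Power is given for a within-subject HRV difference, with one pair on the half or more "of subjects expected to report alcohol use and IPV". The comparison episode is not named.
- **Strengths and Limitations of Design.** This section refers back to analyses above it and to exploratory analyses of whether answering EMA and feasibility queries changes outcomes. No Aim 1 model is visible in the supplied file.
- **Participants.** Adjustment for drug use is allowed if needed; alcohol is not mentioned there.

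**The concern.** The reference episodes contain neither drinking nor IPV. If the hypothesis is read jointly, as the power paragraph's wording suggests, the difference carries the alcohol effect, the IPV effect and their interaction together. If it is read as two comparisons (drinking against neither, IPV against neither), the IPV comparison still carries the alcohol effect to the extent that IPV episodes include drinking.

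The long-term goal is to recognise times of raised risk of alcohol-facilitated IPV, so that biofeedback can be offered at those times, and the results are to shape the next trial. A signal that responds to any drinking could satisfy the stated hypothesis and still be weak support for that use.

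**Working it through.** **1. What each contrast estimates.** Let A mark drinking and I mark IPV in an episode, with

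HRV = a + bA·A + bI·I + bAI·A·I + error.

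- Both versus neither: bA + bI + bAI.
- Drinking with IPV versus drinking without IPV: bI + bAI.

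The two differ by bA, the effect of drinking without IPV. If bI = bAI = 0, the first contrast equals bA and the second equals zero.

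**2. The plan's own figures.** With two partners per couple, effective N = 100/(1 + ICC). This gives 100/1.1 = 90.9 and 100/1.3 = 76.9, matching the stated 90 and 76. The stated detectable difference of d = 0.3 at 80% power (two-sided, alpha 0.05) needs 90 pairs on the paired-difference scale (power 80.4%). With 50 pairs the detectable difference is 0.40 and power at 0.3 is 55%. The stated figure would be met at 50 pairs only if d is on the raw-SD scale with an unstated within-person correlation of about 0.73. That mismatch is a separate matter, and this point does not depend on it.

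**3. Effective pairs.** Half of 100 participants is 50 people, in 25 couples if both partners contribute. Effective pairs = 50/(1 + ICC): 50 at ICC 0, about 45 at 0.1, about 38 at 0.3, and 25 at 1.

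**4. How often drinking alone would make the stated contrast significant.** The documents give no size for the alcohol effect on HRV, so d is assumed; the IPV effect is set to zero and each person gives one pair. Power is from the noncentral t with n − 1 degrees of freedom and noncentrality d·√n.

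| Assumed alcohol effect d | n = 25 | n = 38 | n = 45 | n = 50 |
|---|---|---|---|---|
| 0.2 | 16% | 22% | 26% | 28% |
| 0.3 | 30% | 44% | 50% | 55% |
| 0.4 | 48% | 67% | 75% | 79% |

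At d = 0.3 the noncentrality is 0.3 × √25 = 1.50 and 0.3 × √50 = 2.12, against critical values of 2.064 and 2.010. Taken at face value, the plan's power statement implies that a difference of 0.3 due to drinking alone would be declared significant 80% of the time.

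**5. The added contrast under the same assumptions.** In 20,000 simulated trials with 50 pairs, alcohol effect 0.3 and no IPV effect, both versus neither was significant in 55% and drinking with versus without IPV in 5%, the nominal rate. This assumes equal drinking in both kinds of episode and no effect of conflict.

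**6. Its precision.** 95% CI half-width = t(0.975, n − 1)/√n: 2.010/√50 = 0.28 and 2.064/√25 = 0.41 SD of the paired difference.

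**7. Its residual confounding.** Suppose the alcohol effect is 0.3 and linear in amount, and IPV episodes involve 1.5 times the drinking (all assumed). The added contrast is then 0.3 × 1.5 − 0.3 = 0.15 with no IPV effect, and is significant 11% (n = 25) to 18% (n = 50) of the time.

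**The case against.** **The construct is the combined state.** The study concerns alcohol-facilitated IPV and promises proof of concept, not separation from drinking. Both versus neither tests that combined state directly. This stands: the contrast is legitimate and should be kept. It does not remove the point, because a marker that responds to any drinking would be weak support for the stated objective.

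**The analysis may exist elsewhere.** A reader might infer that the study has no Aim 1 model, or that it never intended to separate drinking from IPV. The documents do not support that. The Strengths and Limitations section points to analyses and exploratory analyses that cannot be seen in this file, and the planned associations among HRV, drinking and IPV could include the missing contrast. What can be said is that nothing in the supplied text commits to it.

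**The added contrast is not clean either.** A reader might infer that drinking with IPV versus drinking without IPV would establish an IPV-specific marker. It would not. The protocol's own mechanism is intoxication plus distress during conflict, and drinking episodes without IPV will often contain no conflict. Non-violent conflict could therefore produce the difference, as could heavier drinking. This objection stands and limits the fix.

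**The percentages are not a measured error rate.** They are power figures at assumed effects with one pair per person, although 4 × 28 = 112 reports are scheduled. This is also right. They illustrate the problem; the case rests on step 1 of the working.

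**Conclusion.** The point holds as a gap in specification, not in data collection. The stated contrast changes drinking and IPV together, the rationale gives reason to expect lower HRV with intoxication, and no drinking-without-IPV comparator is committed to in the supplied text. On that contrast alone, a positive finding cannot distinguish a marker of drinking from a marker of alcohol-facilitated IPV. This is so under either reading of the hypothesis, to the extent that IPV episodes include drinking.

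The size is illustrative: 30% to 55% significant at an assumed alcohol effect of d = 0.3 with no IPV effect, one pair per person and 25 to 50 effective pairs. The rationale names intoxication and IPV together and sizes neither, so the true figure is unknown.

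It would go too far to call the hypothesis invalid or to say that the study cannot address the question. Drinking, conflict and affect are reported at each EMA prompt, and HRV is summarised for each 4-hour period.

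**What to change.** Keep both versus neither. In the hypotheses and in Statistical Analyses:

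- Add, as a pre-specified secondary estimate, the within-person contrast of HRV in drinking episodes with IPV versus drinking episodes without IPV. Take it from one model with alcohol, IPV and their interaction, with standard errors clustered by couple.
- Report drinking episodes with non-violent conflict as a further comparator, or adjust for conflict and affect in a sensitivity analysis.
- State whose drinking and whose IPV define an episode: self or partner, perpetrated or received. Both partners are enrolled and report on both, so this is otherwise open.
- Report all contrasts side by side with 95% CIs. Do not describe HRV as specific to IPV on both versus neither alone, and treat the added contrast as supportive and not conclusive, because conflict and amount drunk may still confound it.
- If an Aim 1 model exists elsewhere, state it here.

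**Cost.** No new data collection is needed, but a model and episode definitions must be written. The added contrast is imprecise (half-width 0.28 to 0.41 SD with 50 to 25 single pairs) and may be inconclusive. It will be wider if fewer participants have both kinds of drinking episode, which is possible because only one partner need have AUD.

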## RESEARCH STRATEGY

**Overview.** The objective of this study is to examine the proximal role of respiratory sinus arrhythmia measure of heart rate variability (HRV) in alcohol-facilitated intimate partner violence (IPV) in naturalistic settings. Our secondary objective is to examine the usability, feasibility, and acceptability of HRV biofeedback (HRV-B) self-administered remotely for seven days in a non-randomized, open-label fashion. Participants will be *50 couples (total N=100)* with AUD and IPV. We will accomplish this by using wearable technology and a mobile application to complete ecological momentary assessment, physiological monitoring, and geolocation for 28 days.

## APPROACH

**Overview.** This 28-day micro-longitudinal study will examine 1) the proximal role of HRV in alcohol-facilitated IPV in naturalistic settings, and 2) preliminary usability, feasibility, and acceptability of HRV-B self-administered via smartphone for 7 days. We will employ a unique combination of EMA, ambulatory physiological monitoring, and geolocation enabled by smartphone and discreet wearable activity trackers.

**Participants.** Participants (*50 couples; total N=100 participants; 50% women with AUD*) ages 21-70 years, any gender identity or sexual orientation, and located in any state in the United States. The primary inclusion criteria are that at least one partner within each dyad must: 1) meet DSM-V diagnostic criteria for current AUD (MINI-7) and current alcohol use based on (TLFB), and 2) report at least one instance of physical IPV in the past two years (assessed via the CTS-2). Additional inclusion criteria: 3) Cognitive functioning sufficient to provide informed consent and participate accurately ( $\geq 26$  on the Mini-Mental Status Exam [MMSE]), 4) married, cohabiting, or in a committed relationship for  $\geq 6$  months, and 5) maintenance of psychotropic medications on a stable dose for at least 4 weeks before study initiation (to minimize pharmacologic effects on HRV). Exclusion criteria: 1) History of or current psychotic, bipolar, or antisocial personality disorders, 2) moderate or severe drug use disorder (e.g., cannabis). Concurrent mild drug use disorders are acceptable because of the marked frequency of co-occurrence among individuals with AUD. Moderate or severe Nonalcoholic Substance Use Disorder is acceptable if there has been no current substance use in the last 1-2 months. Drug use will be measured (via urine drug screen, TLFB, and EMA) and controlled for in statistical analyses if needed. 3) Alcohol withdrawal as indicated by CIWA-Ar score  $>8$ , 4) current suicidal or homicidal ideation and intent, 5) serious cardiovascular conditions (e.g., pacemaker, *cardiac arrhythmia, hypertension*) *because the safety of HRV-B has not been established in these populations*, 6) use of medications such as lithium, methadone, alpha or beta blockers or cholinergic/ anticholinergic drugs likely to confound normative cardiovascular responding, 7) current neurologic conditions (i.e., *Parkinson's disease*) or history of traumatic brain injury, 8) severe and unilateral IPV in the past 6 months (for safety), 9) current pregnancy. Pregnancy may cause discrepancies in heart rate that are not attributable to the study intervention which may present a confound for resulting theoretical findings.

**Recruitment.** *We need to enroll 2-3 couples per month with AUD and recent IPV in order to meet our target recruitment goal.* We will receive clinician referrals from MUSC's Center for Drug and Alcohol Programs (CDAP) and community providers in any state in the United States. The PI and CO-Is will utilize new and existing relationships with colleagues for referrals in state and out of state.

In addition, we will post IRB approved recruitment flyers in other MUSC and community treatment clinics and catchment areas. The study team will receive all required approvals before posting flyers outside of MUSC. This may include asking permission from clinics, restaurants, or other community areas. Advertisements will be placed on the internet (e.g., Craigslist and SCresearch.org) and will target in state and out of state participants. Participants who refer others to the study will be compensated \$10 per randomized referral, allowing us to reach a wider pool of potential participating couples including couples from the community with IPV and AUD, in addition to treatment-seeking couples with IPV and AUD. Further, participants from past MUSC research studies who have consented to be contacted for future research studies will be recruited via telephone screening and/or e-mails. These individuals will be referred to us via other MUSC researchers, or they may have indicated consent

to be contacted about future research studies within the research group. The research team has used these methods successfully to recruit patients to clinical and laboratory studies.

Chart review and EPIC lists will be used for recruitment to find potential participants that have been identified as struggling with alcohol use or diagnosed with Alcohol Use Disorder. The study team will use an IRB approved letter and script to inform identified individuals about our study.

Potential participants will be asked to complete an online screener. Potential participants may also be sent a recruitment email that includes details about the study (e.g., time requirement, basic inclusion criteria, compensation), a link to the IRB approved screener, and contact information for the research team will be included in the email. Potential participants will also be contacted via phone.

**Setting.** All procedures will be conducted on the MUSC campus. Procedures can also be conducted via telehealth. Since this is an observational study, participants will engage in research assessments in their natural environment.

**Telehealth.** We are equipped to conduct the full scope of this project remotely, enabling us to enroll participants outside of our immediate geographic area, and outside the state of South Carolina. Participants in this research study may choose to complete this study via home-based telehealth (HBT) care (i.e., service delivery to patients in their homes using consumer-friendly, video-conferencing technology) which may likely enhance retention by directly circumventing financial and transportation barriers associated with traveling to MUSC for in-person sessions. Further, telehealth allows the study team to recruit and enroll participants who are located outside of the state of South Carolina (inside US). HBT sessions will be delivered via standard desk, laptop computer, tablet, or smartphone running MUSC approved applications. Participants who choose telehealth will be required to have their own computer, tablet, or smartphone; to complete the study sessions however, a cell phone containing the required application may be provided to MUSC participants for the duration of the study as needed. Participants must consent to the shipment and receipt of study supplies in order to complete the study via telehealth, including pregnancy test, breathalyzer test, study supplies, consent, materials for UDS, HIPAA, and other study documents when necessary. Study materials will be shipped overnight by research staff to participant's designated location at the agreed upon date using overnight shipping with contracted shipping company (FedEx, UPS).

Prior to the screening appointment the study team will mail any necessary study documents, pregnancy tests and alcohol saliva strips to test for pregnancy and recent alcohol use. The alcohol saliva strip must read white (indicative of 0.00 BAC to validate the consent and prior to completing any study procedures. Further, prior to proceeding, females will be asked to take a pregnancy test and must provide verbal confirmation of a negative pregnancy test prior to proceeding with the screening appointment. At each visit, in lieu of a Breathalyzer Test, an Alcohol Saliva Test will be used to measure blood alcohol concentration (BAC) for telehealth visits. In front of the camera, participants will open the one time use test strip, place strip on tongue for 10 seconds, then hold test strip and a color chart to the camera for a study team member to assess. Samples reading >0.01 g/dl will be considered positive. The pregnancy tests used in this study are designed for at-home use, come with clear and simple instructions. In very rare and highly unlikely circumstances where the participant is unfamiliar with how to provide a urine sample or take an at-home pregnancy test, study staff can provide further instructions on how to provide a urine sample, how use the dipstick to test, and to differentiate between a positive and negative result. Ability and willingness to perform an at-home pregnancy test is required for telehealth female participants.

All telehealth participants complete a participant locator form with study staff, that allows the study team to identify local emergency care facilities and contact information. Specifically, for out of state or remote participants, the study staff will compile a list of referrals and emergency contacts to provide to study participants ahead of enrollment.

**Eligibility Assessment.** Following preliminary phone screening, those who elect in-person participation will complete private written informed consent apart from their partner, a breathalyzer, urine drug screen, and baseline eligibility assessment (Table 1). Remote participants will be mailed a study packet including written telehealth policies, procedural telehealth instructions for meeting with research staff, UDS cup and saliva alcohol strips, and a hard copy of the informed consent form ahead of their baseline assessment. Electronic informed consent, eligibility interviews, and sample readings will take place via videoconferencing (via Doxy.me) with research staff. Research staff always establish contact information for safety and that the participant is able to participate with privacy from other household members before beginning. All participants will complete self-report surveys via RedCap. Remote participants will receive a RedCap link via email or text to complete their baseline surveys online on their home computer, tablet, or smartphone. Eligible remote participants who choose to enroll will be mailed written instructions regarding how to use study equipment and complete EMA surveys, an activity tracker and charger, mobile device (if needed), and written HRV-B breath pace training script based on published protocol. All participants will receive HRV-B and EMA training via telehealth or in-person with research staff. Ineligible participants will be provided with community and treatment resources.

